2. SYNOPSIS

Study Identifier	ONSET
Study Title	ON-treatment Single-cell analysis for the identification of Early Tumor response biomarkers on prospective collected serial tumor biopsies in Triple Negative Breast Cancer patient during standard neoadjuvant chemo-immunotherapy
Protocol Version and Date	V 1.1 10-Feb-2026
Sponsor	IRCCS Ospedale San Raffaele

Funding Source(s)	Medical Oncology Unit internal funding (Eredità Buffa)
Principal Investigator	[name] Medical Oncology IRCCS Ospedale San Raffaele
Study Description	
This exploratory translational study investigates early breast cancer (EBC), focusing on triple-negative (TNBC) and high-risk luminal (ER+/HER2-) subtypes. By integrating single-cell RNA sequencing, using the 10x Genomics platform (or similar technologies if it will be not available at the time of experiment), and spatial imaging analyses from serial tumor biopsies, the project aims to characterize tumor-immune interactions and identify predictive biomarkers of response or resistance to neoadjuvant chemo-immunotherapy.
 
We hypothesize that early molecular and spatial features, when detected at the single-cell level, can predict treatment sensitivity or resistance. This would enable adaptive therapeutic strategies that minimize overtreatment while maximizing efficacy in EBC. Our goal is to reveal, for the first time, the cellular heterogeneity and spatial interactions that drive therapy resistance and disease progression.
 
The analysis will be performed on tumor biopsies collected before the start of treatment, after C1D1 and on surgical material. The only tissue sample collected specifically for the study is the biopsy after C1D1.

Study Design	
This is an interventional translational, single-center study with a prospective, longitudinal cohort design based on serial tumor tissue collection and analysis for the identification of early tumor response biomarkers. Tumor samples will be obtained at three predefined time points: (i) prior to initiation of treatment (baseline biopsy), (ii) after Cycle 1 Day 1 (C1D1) of therapy, and (iii) at the time of surgery (surgical specimen). Among these, the only biopsy performed specifically for study purposes is the post-C1D1 biopsy; the baseline and surgical samples are collected as part of standard clinical management with no differences expected among the procedures. Analyses will focus on temporal molecular and histopathological changes across serial samples to characterize treatment-related tumor evolution.

Primary Objective To characterize the dynamic changes in tumor and immune cell populations in TNBC and to prospectively collect serial samples from high-risk luminal (ER+/HER2-) breast cancer patients.	Primary Endpoint Gene expression levels per single-cell and relative cell clustering (%)	Timepoints Pre-treatment, on-treatment (after first cycle of therapy), and post-treatment (surgery or residual disease)
Exploratory Objectives To correlate single-cell gene expression data with pCR and RD to identify predictive signatures of therapy response	Other pCR and RD	Timepoints Across all collected timepoints
Study Population	Adult female patients (≥ 18 years) with early breast cancer, triple negative or high-risk luminal (ER+/HER2) subtypes, candidate to receive SOC neoadjuvant chemo/immunotherapy	
Inclusion Criteria	
 Female patients aged ≥ 18 years. ECOG performance status 0–1. Histologically confirmed early breast cancer with one of the following molecular profiles: 
 TNBC: ER and PR negative (IHC $<10\%$) and HER2 negative (IHC 0–1+ or FISH non-amplified). High-risk luminal (ER+/HER2-): ER positive (IHC $\geq 10\%$) HER2 negative (IHC 0–1+ or FISH non-amplified), with high-risk features (e.g., Grade 3, PR-negative, high proliferation, high TILs). Clinical indication for neoadjuvant treatment according to standard practice: 
 TNBC: cT1c and/or cN positive, or cT2 (>2 cm) and/or cN positive (stage II,III). High-risk luminal: features as defined above (Grade 3, PR-negative, high proliferation, ER low). Ability to understand and sign written informed consent for participation in the study, approved by the local Ethics Committee. 	
Exclusion Criteria	
 HER2-positive tumors. 	

	2. Multifocal tumors — exclusion if a single index lesion cannot be identified and sampled; otherwise allowed if a representative lesion can be biopsied. 3. Known metastatic disease. 4. Clinical contraindications to the planned neoadjuvant therapy. 5. Decision for upfront surgery as determined by the multidisciplinary team. 6. Inability to provide informed consent. 7. Pregnancy or breastfeeding. 8. Prior systemic therapy (chemotherapy, immunotherapy, or endocrine therapy) for the current breast cancer before baseline biopsy 9. On-treatment biopsy clinically not feasible or contraindicated
Intervention(s)	

Patients will receive standard-of-care neoadjuvant chemotherapy according to sequential anthracycline and taxane regimens. In addition, patients with triple-negative breast cancer (TNBC) will receive immunotherapy with pembrolizumab as per the KEYNOTE-522 schema. No modifications to the SOC treatments need to be reported.
 
Patients enrolled in the study will undergo a single on-treatment biopsy after the first cycle of neoadjuvant therapy, that is not required as per SOC, and two biopsies (at diagnosis and at surgery) already planned for clinical practice to assess biomarkers predictive of early response/progression with single-cell sequencing technique.
	
Intervention for Biomarker identification	The study will analyze fresh biopsies collected from TNBC patients receiving standard neoadjuvant chemo-immunotherapy at OSR. The samples will be collected at three timepoints (pre-treatment, on-treatment (after the first cycle), and after-treatment (in cases with presence of viable tumor cells in the post-treatment/surgical tissue specimen as Residual Disease). In particular, single-cell RNA sequencing (scRNA-seq) of TNBC biopsies will be performed, and the scRNA-seq data will be analyzed to characterize the dynamic molecular landscape of the tumor and immune system using the 10x Genomics platform (or similar technologies if it will be not available at the time of experiment).
Safety Criteria	The breast biopsy performed for study purposes does not pose any safety concerns, as it follows standard clinical procedures with minimal risk to participant and being minimally invasive

Efficacy Criteria	The potential clinical utility of on-treatment biopsy to further inform clinical management of the patient is an exploratory objective of this project
Sample Size	
We plan to prospectively enroll 55 patients (20 TNBC and 35 Luminal BC).
 
For the cohort of TNBC, we will collect biopsies from 20 patients at 3 different timepoints (baseline, after C1, surgery).
 
For the cohort of Luminal BC, we expect to collect tissue samples from 35 patients at 3 different timepoints (baseline, after C1, surgery)

Statistical Design	
Given the translational and exploratory nature of this study, which primarily aims to understand tumor-immune interactions and identify potential predictive biomarkers, a formal statistical plan and power calculation are not applicable. Descriptive statistics and exploratory analyses will be performed, applying appropriate methods to account for multiple testing where relevant. These analyses will include the identification of transcriptional programs, cellular states, and spatially resolved cellular distributions associated with treatment response. Multi-modal data integration approaches (e.g., clustering, dimensionality reduction, and machine-learning-based modeling) will be applied to derive candidate predictive signatures. Correlations between molecular, spatial, and clinical variables will be assessed to explore potential biological mechanisms of sensitivity or resistance to therapy. The resulting exploratory signatures or models will be evaluated for their association with treatment response and relevant clinical outcomes (pCR).

Duration of the Study	
Duration of enrollment: From January 2026 to December 2028
 
Duration of treatment: about six months
 
Duration of subject participation: 1 year
 
Duration of total study period: 5 years

3. ABBREVIATIONS AND DEFINITIONS

3.1. Abbreviations.

CRF	Case Report Form
CRO	Contract Research Organization
CTC	Clinical Trial Center
DPIA	Data Protection Impact Assessment
EC	Ethics Committee
GCP	Good Clinical Practice
ICF	Informed Consent Form
ICH	International Conference on Harmonization
LVLP	Last Visit of Last Patient
OSR	Ospedale San Raffaele
PI	Principal Investigator
ADCs	Antibody–drug Conjugates
AIRC	Associazione Italiana per la Ricerca sul Cancro
BC	Breast Cancer
eBC	Early Breast Cancer
ER	Estrogen Receptor
HER2	Human Epidermal growth factor Receptor 2
pCR	Pathologic Complete Response
PgR	Progestinic Receptor
RD	Residual Disease
sTILs	Stromal Tumor-Infiltrating Lymphocytes
TNBC	Triple–Negative Breast Cancer
scRNA–seq	Single Cell RNA sequencing

3.2. Definitions

RD	Presence of viable tumor cells in the post-treatment tissue specimen
pCR	Absence of viable tumor cells

4. BACKGROUND AND RATIONALE

Over recent decades, prognosis and cure rates in early breast cancer (eBC) have improved due to new treatments, including immunotherapy, antibody-drug conjugates (ADCs), and targeted therapies such as CDK4/6 and PARP inhibitors. However, most were introduced empirically, often leading to unnecessary treatments and associated toxicities, while a significant proportion of patients still experience recurrence.

In triple-negative breast cancer (TNBC), pembrolizumab added to neoadjuvant chemotherapy (KEYNOTE-522)¹ increased pathological complete response (pCR) rates and event-free survival, now forming a standard of care. Patients without pCR may receive adjuvant capecitabine or continued immunotherapy, although optimal post-neoadjuvant strategies remain under investigation. For patients with germline BRCA1/2 mutations, adjuvant olaparib (Olympia)² improves disease-free and overall survival, supporting PARP inhibitor-based tailored strategies in TNBC and high-risk luminal eBC (CPS+EG ≥ 3). In hormone receptor-positive (HR+) breast cancer, adding CDK4/6 inhibitors to adjuvant endocrine therapy (MonarchE, NATALEE)^{3,4} improves invasive disease-free survival in high-risk patients. Ongoing studies also explore immunotherapy in the neoadjuvant setting (CheckMate-7FL, KEYNOTE-756)^{5,6}, reflecting a trend toward intensifying treatment in biologically high-risk luminal disease. ADCs, which selectively deliver cytotoxic agents to tumor cells, are being evaluated in both neoadjuvant and adjuvant settings. Trials such as TROPION-Breast03 and TROPION-Breast04 are investigating datopotamab deruxtecan in TNBC to optimize treatment intensity^{7,8}.

The dual challenge of avoiding overtreatment in low-risk patients while optimizing outcomes in high-risk patients has led to a growing emphasis on refining treatment strategies through biologic and molecular stratification. Prognostic and predictive information can be derived from pre-treatment and on-treatment core biopsies, as well as from residual disease (RD) after neoadjuvant therapy. In triple-negative breast cancer (TNBC), we already have data of an extensive molecular characterization of pre-treatment, on-treatment (after the first cycle of therapy) and post-treatment samples from patients enrolled in the NeoTRIP trial⁹⁻¹², a randomized Phase III trial that compared neoadjuvant carboplatin and nab-paclitaxel with or without the anti-PD-L1 atezolizumab⁹. These data showed that stromal tumor-infiltrating lymphocytes (sTILs) and several tumor and immune-related biomarkers were predictive of pathologic complete response (pCR) and RD. Particularly, response to therapy was best predicted by combining tissue features before and on-treatment, pointing to a role for early biopsies in guiding adaptive therapy. However, bulk mRNA expression does not consider intratumor heterogeneity in terms of single cell expression and spatial tissue organization. In a recent publication in Nature, we performed an analysis by imaging mass cytometry demonstrating the relevance of spatial organization and type and functional state of immune cells in precision immunology. Single-cell analysis by RNA-seq may contribute to better characterize these tumor and immune cell populations, providing insights into mechanisms of

response and resistance to therapy and guiding the development of the next generation of chemo/immune combinations^{13,14}. In addition, in luminal breast cancer (ER+/HER2-) we have recently identified a distinct molecular subset characterized by high proliferation and low ER-related signaling with unique molecular features that may have important therapeutic implications¹⁵. In particular, biomarker analyses and clinical data suggest a potential role for immunotherapy in this group.

Given these data in the present study we will enroll a cohort of patients with stage II-III early triple negative breast cancer, candidate to receive neoadjuvant chemo-immunotherapy and a cohort of patients with High-risk luminal (ER positive/HER2 negative) breast cancer with high-risk features (Grade 3, PR-negative, high proliferation, high TILS). The aim is to identify in these specific populations of patients useful predictive and prognostic biomarkers potentially useful in clinical practice to tailor therapy dynamically based on individual tumor biology and response, balancing escalation and de-escalation of therapies.

We plan to prospectively enroll a total of 55 patients, comprising 20 patients with TNBC and 35 patients with high-risk luminal breast cancer. For the cohort of TNBC, we will collect biopsies from 20 patients at 3 different timepoints (baseline, after C1, surgery). For the high-risk luminal cohort, we expect to collect tissue samples from 35 patients at 3 different timepoints (baseline, after C1, surgery)

5. RISK/BENEFIT ASSESSMENT

This is an interventional clinical study in which all diagnostic and therapeutic procedures are part of standard clinical practice, except for one additional research-related procedure: an on-treatment tumor biopsy. The study therefore carries minimal incremental risk for participants

5.1. Known Potential Risks

The only additional procedure beyond routine clinical management is the on-treatment tumor biopsy, performed for translational research purposes. Potential risks are therefore limited to those commonly associated with standard biopsy procedures, as reported in the literature and routine clinical practice.

- Immediate risks: Local pain, mild bleeding, bruising, and risk of infection at the biopsy site. In rare cases, more significant complications such as hematoma or delayed wound healing may occur. These risks are minimized by performing the biopsy under sterile conditions by experienced personnel, with appropriate post-procedural monitoring.
- Long-term risks: Long-term adverse effects are not expected. Scarring at the biopsy site may persist but is usually minimal and clinically insignificant.

- Alternative procedures: No less invasive alternatives could provide the same type of tissue material necessary for the planned molecular and histopathological analyses. Peripheral blood or imaging data cannot fully replace the biological information derived from tumor tissue. Therefore, the on-treatment biopsy is justified as the only additional procedure needed to achieve the study objectives.

5.2. Known Potential Benefits

Participants are not expected to derive direct therapeutic benefit from study participation, as the protocol does not modify clinical treatment or management and the purpose is translational and exploratory. However, there are potential indirect benefits for participants:

- Immediate potential benefits: participants may receive additional clinical assessments and closer monitoring at the time of biopsy, which may incidentally contribute to improved documentation of treatment response.
- Long-term potential benefits: The information obtained from the molecular and histopathological analyses of the on-treatment biopsy may improve scientific understanding of treatment response and resistance mechanisms. These results could contribute to the development of more effective and personalized therapeutic strategies of early escalation/descalation for future patients with the same disease.

5.3. Assessment of Risks and Benefits ratio

The study exposes participants only to the minimal incremental risk associated with one additional biopsy, a procedure commonly performed in oncology with a low complication rate. All reasonable measures have been implemented to minimize risk, including strict adherence to sterile technique and safety procedures, performance by trained medical staff, exclusion of patients for whom biopsy poses a medical contraindication, and immediate post-biopsy clinical observation.

Given the limited and well-controlled risk, and the high potential value of the biological data to advance knowledge on treatment mechanisms, the overall risk-benefit ratio is considered favorable. The anticipated scientific and societal benefits clearly outweigh the minimal additional risk to individual participants.

6. OBJECTIVES AND ENDPOINTS

Primary Objective	Primary Endpoint	Timepoints
-------------------	------------------	------------

To characterize the dynamic changes in tumor and immune cell populations in TNBC and to prospectively collect serial samples from high-risk luminal (ER+/HER2-) breast cancer patients	Gene expression levels per single-cell and relative cell clustering (%)	Pre-treatment, on-treatment (after first cycle of therapy), and post-treatment (surgery or residual disease)
Exploratory Objectives To correlate single-cell gene expression data with pCR and RD to identify predictive signatures of therapy response	Other pCR and RD	Timepoints Across all collected timepoints

7. STUDY DESIGN

This exploratory interventional translational study investigates early breast cancer (EBC), focusing on triple-negative (TNBC) and high-risk luminal (ER+/HER2-) subtypes. By integrating single-cell RNA sequencing and spatial imaging analyses from serial tumor biopsies, the project aims to characterize tumor-immune interactions and identify predictive biomarkers of response or resistance to neoadjuvant chemo-immunotherapy⁹⁻¹².

The hypothesis of this study is that early molecular and spatial features identified at the single-cell level can predict therapeutic response or resistance in patients with early breast cancer, enabling adaptive, personalized treatment strategies that minimize overtreatment while maximizing efficacy. To test this hypothesis, we will conduct a translational study with a prospective longitudinal cohort design. The study is based on the existing retrospective experience with TNBC samples from the NeoTRIP trial⁹. Moreover we will prospectively collect serial tumor samples from high-risk luminal (ER+/HER2-) patients supported by the evidences already reported in the background. Two main patient cohorts will be included, TNBC and high-risk luminal breast cancer, and each participant will be followed from baseline (pre-treatment biopsy) through on-treatment (after the first cycle) to surgery (post-treatment or residual disease). The expected duration of participant involvement is approximately six months, according to the neoadjuvant treatment schedule. The study is monocentric, conducted at Ospedale San Raffaele, with collaborative contributions from SR-TIGET and Cambridge University for advanced single-cell and spatial analyses. No formal interim analysis is planned

due to the exploratory and hypothesis-generating nature of the study, and data will be analyzed descriptively, with integrative analyses performed as samples become available. Data will be collected through serial tumor biopsies processed for single-cell RNA sequencing and spatial imaging technologies, and clinical and pathological outcomes including pCR (defined as absence of tumor infiltrating cells in the surgical sample) and residual disease status (defined as presence of viable tumor cells in the post-treatment tissue/surgical specimen) will be recorded from medical records. This approach allows high-resolution, multi-modal characterization of tumor and immune landscapes and is essential to address the study objectives. Any future research on previously stored biological material will require approval by the Ethics Committee prior to initiation, in accordance with local and international regulations.

7.1. Study duration

Duration of enrollment: 3 years

Duration of treatment: about six months

Duration of total follow-up: one year

Duration of total study period: 5 years

8. STUDY POPULATION

8.1. Study Participants

We plan to prospectively enroll a total of 55 patients, comprising 20 patients with TNBC and 35 patients with high-risk luminal breast cancer. For the cohort of TNBC, we will collect biopsies from 20 patients at 3 different timepoints (baseline, after C1, surgery). For the high-risk luminal cohort, we expect to collect tissue samples from 35 patients at 3 different timepoints (baseline, after C1, surgery)

8.2 Inclusion Criteria

Patients eligible for the present study would have the following inclusion criteria:

1. Female patients aged ≥ 18 years.
2. ECOG performance status 0–1.
3. Histologically confirmed early breast cancer with one of the following molecular profiles:
 - TNBC: ER and PR *negative* (IHC $<10\%$) and HER2 *negative* (IHC 0–1+ or FISH non-amplified).
 - High-risk luminal (ER+/HER2-): ER *positive* (IHC $\geq 10\%$) HER2 *negative* (IHC 0–1+ or FISH non-amplified), with high-risk features (e.g., Grade 3, PR-negative, high proliferation, high TILs).
4. Clinical indication for neoadjuvant treatment according to standard practice:
 - TNBC: cT1c and/or cN positive, or cT2 (>2 cm) and/or cN positive (stage II, III).

- High-risk luminal: features as defined above (Grade 3, PR-negative, high proliferation, ER low).

5. Ability to understand and sign written informed consent for participation in the study, approved by the local Ethics Committee.

8.3 Exclusion Criteria

Patients will be excluded from the study if they meet one or more of the following criteria:

1. HER2-positive tumors.
2. Multifocal tumors — exclusion if a single index lesion cannot be identified and sampled; otherwise allowed if a representative lesion can be biopsied.
3. Known metastatic disease.
4. Clinical contraindications to the planned neoadjuvant therapy.
5. Decision for upfront surgery as determined by the multidisciplinary team.
6. Inability to provide informed consent.
7. Pregnancy or breastfeeding.
8. Prior systemic therapy (chemotherapy, immunotherapy, or endocrine therapy) for the current breast cancer before baseline biopsy
9. On-treatment biopsy clinically not feasible or contraindicated

8.4 Screening Failures

Participants who provide written informed consent to participate in the study but are found not to meet one or more eligibility criteria during the screening procedures will be considered screen failures. For transparency and accurate reporting, minimal information will be collected for all screen failure participants, including demographic data, details of the screening process, and the specific eligibility criteria that were not met. This information will help ensure proper documentation of the study population and support the interpretation of study results.

9. STUDY INTERVENTIONS

Patients will receive standard-of-care neoadjuvant chemotherapy according to sequential anthracycline and taxane regimens as per standard guidelines. In addition, patients with triple-negative breast cancer (TNBC) will receive immunotherapy with pembrolizumab as per clinical practice (as the KEYNOTE-522 schema). The prescription of these treatments is entirely independent of the decision to include the patient in the study, and all medications are used within their approved indications and as part of routine clinical practice. The study includes one additional research-related procedure (the on-treatment biopsy after C1D1) beyond standard

clinical practice: an on-treatment tumor biopsy. No difficulties are anticipated in performing the on-treatment biopsy; however, should the procedure not be feasible for any reason, the patient will be considered a screen failure.

All therapeutic indications and diagnostic assessments, including baseline imaging, laboratory tests, and follow-up evaluations, are part of the patient's routine clinical management and are conducted according to institutional guidelines and the treating physician's discretion.

Follow-up visits correspond to routine care or national and international guideline requirements.

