10.1. Efficacy Criteria

The efficacy of the study procedure will be defined in relation to the technical and biological success of the on-treatment biopsy (.especially in terms of sample adequacy)

No clinical efficacy endpoints are foreseen.

10.2.Safety Criteria

 I.R.C.C.S. Ospedale San Raffaele	ONSET trial Protocol	Date: 10/02/2026 Version: 1.1
---	-----------------------------	----------------------------------

Safety evaluation will focus on potential adverse events (AEs) related to the biopsy procedure, since no investigational drug or device is used in this study. All AEs will be collected from the time of the biopsy until the next scheduled clinical evaluation or up to 30 days post-procedure.

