11.3. Subject Identification

Participants are considered enrolled once informed consent is signed by the patient or their legal representative. Each participant will receive a unique study code (e.g., ON_TN_XX; where ON_TN is the abbreviation of the Protocol Code, XX is the progressive subject number in increasing order starting from 01) for tracking, and a confidential list linking codes to identities will be maintained at the study site.

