12.1 Discontinuation of study Intervention

Discontinuation from <study intervention> does not mean discontinuation from the study, and remaining study procedures should be completed as indicated by the study protocol. This may happen for a number of reasons, including but not limited to:

The occurrence of what the participant perceives as an intolerable AE.

Inability to comply with study procedures

Participant decision

Participants may choose to stop treatment and/or study assessments but may remain on study follow-up.

If a clinically significant finding is identified (including, but not limited to changes from baseline) after enrollment, the investigator or qualified designee will determine if any change in participant management is needed. Any new clinically relevant finding will be reported as an adverse event (AE).

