16.3 Analysis Populations

All enrolled participants who meet inclusion and exclusion criteria and provide tissue samples at the defined time points will be included in the analyses. Participants who withdraw consent or whose samples are unsuitable will be excluded from molecular and immune profiling, but will remain in descriptive summaries of patient characteristics. No additional selection criteria will be applied.

This study is exploratory and primarily descriptive. Analyses will summarize patient characteristics, sample collection, and molecular/immune profiling results using descriptive statistics. Exploratory analyses of primary and secondary endpoints will be conducted with appropriate statistical methods, including adjustments for multiple testing. No formal hypothesis testing or sample size calculation will be performed, reflecting the translational nature of the study.

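### Section 9 makes a patient a screen failure when her on-treatment biopsy proves infeasible after treatment has begun, which contradicts Section 8.4 and drops infeasible cases from the biopsy-success denominator

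*Protocol*

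**What the plan says.** Section 9 expects no difficulty with the on-treatment biopsy, then adds that "should the procedure not be feasible for any reason, the patient will be considered a screen failure". Section 9.1 places the biopsy during systemic therapy, after one cycle. The schedule in Section 11 puts it on day 3-18 (+/-2), with C1 on day 0, screening on day -28 and the eligibility assessment in the enrolment column only.

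Other sections bear on the same patient:

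- Section 8.4 defines screen failures as consenting participants "found not to meet one or more eligibility criteria during the screening procedures will be considered screen failures". The data kept on them are described as minimal, "including demographic data, details of the screening process, and the specific eligibility criteria that were not met".
- Section 8.3, criterion 9, excludes patients for "On-treatment biopsy clinically not feasible or contraindicated".
- Section 11.3: "Participants are considered enrolled once informed consent is signed".
- Section 12.1 says that stopping the study intervention "does not mean discontinuation from the study, and remaining study procedures should be completed".
- Section 16.3 treats two groups alike, withdrawals and unusable samples. Of the second it says that those "whose samples are unsuitable will be excluded from molecular and immune profiling, but will remain in descriptive summaries of patient characteristics".
- Section 10.1 defines efficacy of the procedure by the "technical and biological success of the on-treatment biopsy", with emphasis on sample adequacy. It gives no denominator.

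**The concern.** A label meant for ineligibility found before treatment is applied to an event that can occur after treatment has started. Three things are at stake.

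1. **Consistency.** Staff cannot apply Sections 8.4, 9 and 12.1 together to a patient who had C1 but no biopsy.
2. **The denominator.** The study's only efficacy criterion is success of this biopsy. If every patient who could not be biopsied becomes a screen failure, feasibility cannot come out below 100%.
3. **The data.** pCR and RD are the outcomes for the exploratory objective, but they are not on the Section 8.4 list. Without them nobody can compare patients with and without the biopsy. The rule covers every cause, which would include a lesion grown too small to sample, early progression, toxicity or refusal. Some of these could be related to response.

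**Working it through.** **Step 1. The order of events.** Consent makes the patient enrolled (11.3). The baseline biopsy precedes therapy (11.5). C1 is on day 0 and the study biopsy on day 3-18 (schedule, Section 11). If infeasibility is seen before C1, Sections 8.4 and 9 agree. If it is seen after C1, Section 9 gives a label that Section 8.4 does not allow.

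**Step 2. The sections side by side for a patient who had C1 but no biopsy.**

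| Section | Status it gives her |
|---|---|
| 8.3, criterion 9 | Excluded if infeasible, but before C1 this can only be a forecast |
| 8.4 | Not a screen failure: nothing was failed during screening |
| 9 | Screen failure |
| 11.3 | Enrolled |
| 12.1 | Remains in the study |
| 16.3 | Not addressed: she has no unsuitable sample and has not withdrawn consent |

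**Step 3. Effect on the success criterion.** The protocol states no infeasibility or adequacy rate. Its only related figure is the sample size, 20 + 35 = 55, which agrees. All rates below are assumptions.

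Success over all who started C1 = (biopsies taken / started C1) x (adequate / biopsies taken). The Section 9 rule sets the first factor to 1 and leaves the second unchanged.

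- *TNBC cohort, 3 of 20 infeasible.* Feasibility is 17/20 = 85%, exact 95% CI 62.1-96.8%. Under the rule it is 17/17 = 100%, with exact lower limit 0.025^(1/17) = 80.5%.
- *All 55 patients, about 90% adequacy among biopsies taken:*

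| Infeasible | Feasibility, all 55 | Feasibility under the rule | Success, all 55 | Success under the rule |
|---|---|---|---|---|
| 3 | 52/55 = 94.5% | 52/52 = 100% | 47/55 = 85.5% | 47/52 = 90.4% |
| 6 | 49/55 = 89.1% | 49/49 = 100% | 44/55 = 80.0% | 44/49 = 89.8% |
| 11 | 44/55 = 80.0% | 44/44 = 100% | 40/55 = 72.7% | 40/44 = 90.9% |

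The combined rate rises by about 5, 10 and 18 points. The last column is simply adequacy among biopsies taken, which the rule does not distort.

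**Step 4. Effect on the pCR/RD mix.** Take 20 TNBC patients with an assumed true pCR of 10/20 = 50%, and remove 2.

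- Both had pCR: 8/18 = 44.4%.
- Both had RD: 10/18 = 55.6%.
- One of each: 9/18 = 50%.

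With 4 removed, the extremes are 6/16 = 37.5% and 10/16 = 62.5%. The direction depends on who is lost, and the documents do not say.

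**Step 5. Will it arise?** P(at least one case) = 1 - (1 - q)^n. At an assumed q = 5% this is 1 - 0.95^55 = 94% in 55 patients and 1 - 0.95^20 = 64% in the TNBC cohort. At q = 2% it is 67% in 55.

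**The case against.** The other side has several good points.

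- **Section 16.3.** A reader might infer that it contradicts Section 9 by keeping such patients in the summaries. It does not. It names withdrawals and unsuitable samples only, and is silent on a biopsy never taken.
- **Section 12.1.** This is generic text with an unfilled placeholder, so the conflict is softer than with Section 8.4. Its reasons do include inability to comply with study procedures and the participant's own decision, and the biopsy is the only study-specific procedure. The inconsistency stands.
- **Section 11.3.** Every screen failure has signed consent, so enrolment alone does not rule out the label. The sharp contradiction lies in the timing set by Section 8.4.
- **The whole success rate.** A reader might infer that it is favourable by construction. Only feasibility is. Section 10.1 stresses adequacy, and patients with unsuitable samples are not made screen failures.
- **Every correlation of a signature with response.** A reader might infer that all are biased by the label. A patient without the on-treatment sample cannot enter an on-treatment analysis under any label, and Section 16.3 separately requires samples at the defined time points. What the label can cost is her outcome and her baseline and surgical data.
- **The pCR rate.** It is not an endpoint to be estimated. Section 10.1 foresees no clinical efficacy endpoint, and pCR/RD serves as an exploratory correlate. Step 4 measures possible selection, not bias in a planned estimate.
- **Recoverability.** Sections 8.4 and 15.1 require screen failures to be documented with the reason, so they could be counted. Nothing puts them in the success denominator, and pCR/RD is not on the list of what is kept.

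These points narrow the concern but do not remove it.

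**Conclusion.** Section 9 is wrong as written. It contradicts Section 8.4, treats as a screen failure a patient whom Section 11.3 counts as enrolled and who has been treated, and is inconsistent with Section 12.1. Criterion 9 does not rescue it: applying that criterion again after C1 turns an eligibility rule into selection on an event after treatment.

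The firm consequence is that feasibility is 100% under the rule whatever the true rate. The possible consequence is loss of pCR/RD and of baseline and surgical data, so that selection cannot be checked. That the lost patients differ in response is plausible, but the documents do not show it, and its direction is unknown. Every magnitude above rests on assumed infeasibility, adequacy and pCR rates.

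This should be fixed. It is not critical, because the study is exploratory and descriptive and no confirmatory claim depends on it. A statistical analysis plan could not fully repair it, since the protocol itself fixes the classification and lists what is kept on screen failures.

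**What to change.** - Section 9: remove the screen-failure sentence, or limit it to infeasibility found before C1.
- Sections 8.3 and 8.4: state that criterion 9 and screen-failure status are settled before C1.
- Add a category for patients who started C1 and have no on-treatment biopsy: enrolled, on-treatment biopsy not obtained. Record the reason and pCR/RD for each.
- Section 10.1: report biopsy feasibility and success over all patients who started C1, with adequacy among biopsies taken shown separately.
- Section 16.3: say how these patients are handled, and let them contribute to the baseline and surgical analyses. Deleting the Section 9 sentence alone is not enough, because 16.3 also requires samples at the defined time points.
- Section 12.1: fill the placeholder and align the text with the above.

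The cost is wording, plus a reason field and an outcome field for a few patients whose pathology result is already in the clinical record. The reported success rate may look less favourable. The change is best made before recruitment goes far, because what is not recorded at the time may be hard to recover.
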